## 8.9. Exposure In Utero

For investigational products within clinical trials and for marketed products, an Exposure In Utero (EIU) occurs if:

- A female becomes, or is found to be, pregnant either while receiving or having been directly exposed to (e.g., environmental exposure) the investigational product, or the female becomes, or is found to be, pregnant after discontinuing and/or being directly exposed to the investigational product (maternal exposure);
- A male has been exposed, either due to treatment or environmental, to the investigational product prior to or around the time of conception and/or is exposed during the partner pregnancy (paternal exposure)

If any trial subject or trial subject's partner becomes or is found to be pregnant while receiving the investigational product, the investigator must submit this information to

Imperial College, Pfizer, MHRA and REC on an EIU Form. In addition, the investigator must submit information regarding environmental exposure to a Pfizer product in a pregnant woman (eg, a nurse reports that she is pregnant and has been exposed to a cytotoxic product by inhalation or spillage) using the EIU Form. This must be done irrespective of whether an adverse event has occurred and within 24 hours of awareness of the pregnancy. The information submitted should include the anticipated date of delivery (see below for information related to induced termination of pregnancy).

Follow-up is conducted to obtain pregnancy outcome information on all EIU reports with an unknown outcome. The investigator will follow the pregnancy until completion or until pregnancy termination and then notify Imperial College, Pfizer, MHRA and REC of the outcome. The investigator will provide this information as a follow up to the initial EIU Form. The reason(s) for an induced abortion should be specified. An EIU report is not created when an ectopic pregnancy report is received since this pregnancy is not usually viable. Rather, a serious adverse event case is created with the event of ectopic pregnancy.

If the outcome of the pregnancy meets the criteria for immediate classification as a serious adverse event (ie, spontaneous abortion, stillbirth, neonatal death, or congenital anomaly [including that in an aborted foetus, stillbirth or neonatal death]), the investigator should follow the procedures for reporting serious adverse events. In the case of a live birth, the “normality” of the newborn can be assessed at the time of birth (ie, no minimum follow-up period of a presumably normal infant is required before an EIU Form can be completed). The “normality” of an aborted foetus can be assessed by gross visual inspection, unless pre-abortion test findings are suggestive of a congenital anomaly. Additional information about pregnancy outcomes that are classified as serious adverse events follows:

- “Spontaneous abortion” includes miscarriage and missed abortion.
- All neonatal deaths that occur within 1 month of birth should be reported, without regard to causality, as serious adverse events. In addition, any infant death after 1 month that the investigator assesses as possibly related to the *in utero* exposure to the investigational medication should be reported.

Additional information regarding the exposure *in utero* may be requested by the investigator. Further follow-up of birth outcomes will be handled on a case-by-case basis (eg, follow-up on preterm infants to identify developmental delays). In the case of paternal exposure, the investigator must obtain permission from the subject’s partner in order to conduct any follow-up or collect any information

## **8.10. Withdrawal Due to Adverse Events (See also Subject Withdrawal)**

Withdrawal due to adverse event should be distinguished from withdrawal due to insufficient response, according to the definition of adverse event noted earlier, and recorded on the appropriate adverse event CRF page. When a subject withdraws due to a

serious adverse event, the serious adverse event must be reported in accordance with the reporting requirements defined below.

### **8.11. Eliciting Adverse Event Information**

The investigator is to report all directly observed adverse events and all adverse events spontaneously reported by the trial subject. In addition, each trial subject will be questioned about adverse events.

### **8.12. Reporting Requirements**

Each adverse event is to be assessed to determine if it meets the criteria for serious adverse event. If a serious adverse event occurs, expedited reporting will follow local and international regulations, as appropriate.

All adverse events will be reported on the adverse event page(s) of the CRF. It should be noted that the form for collection of serious adverse event information is not the same as the adverse event CRF. Where the same data are collected, the forms must be completed in a consistent manner. For example, the same adverse event term should be used on both forms. Adverse events should be reported using concise medical terminology on the CRFs as well as on the form for collection of serious adverse event information.

#### **8.12.1 Serious Adverse Event Reporting Requirements**

If a serious adverse event occurs, Imperial College, Pfizer, MHRA and REC are to be notified within 24 hours of awareness of the event by the investigator. In particular, if the serious adverse event is fatal or life-threatening, notification to Imperial College, Pfizer, MHRA and REC must be made immediately, irrespective of the extent of available adverse event information. This timeframe also applies to additional new information (follow-up) on previously forwarded serious adverse event reports as well as to the initial and follow-up reporting of EIU cases.

In the rare event that the investigator does not become aware of the occurrence of a serious adverse event immediately (eg, if an outpatient trial subject initially seeks treatment elsewhere), the investigator is to report the event within 24 hours after learning of it and document the time of his/her

For all serious adverse events, the investigator is obligated to pursue and provide information to Imperial College, Pfizer, MHRA and REC in accordance with the timeframes for reporting specified above. In addition, an investigator may be requested by Imperial College, Pfizer, MHRA and REC to obtain specific additional follow-up information in an

expedited fashion. This information may be more detailed than that captured on the adverse event case report form. In general, this will include a description of the adverse event in sufficient detail to allow for a complete medical assessment of the case and independent determination of possible causality. Information on other possible causes of the event, such as concomitant medications and illnesses must be provided. In the case of a subject death, a summary of available autopsy findings must be submitted as soon as possible to Imperial College, Pfizer, MHRA and REC or its designated representative.

### **8.12.2. Non-Serious Adverse Event Reporting Requirements**

Non-serious adverse events are to be reported on the adverse event CRFs, which are to be submitted to Imperial College, Pfizer, MHRA and REC. It should be noted that the form for collection of serious adverse event information is not the same as the adverse event CRF. Where the same data are collected, the forms must be completed in a consistent manner. For example, the same adverse event term should be used on both forms. Adverse events should be reported using concise medical terminology on the CRFs as well as on the form for collection of serious adverse event information.

### **8.13. Suspected Unexpected Serious Adverse Reaction (SUSAR)**

Any suspected adverse reaction related to Axitinib that is both unexpected and serious is to be reported within 24 hours of awareness of the reaction by the investigator. In particular, if the serious adverse reaction is fatal or life-threatening, notification to Imperial College, Pfizer, MHRA and REC must be made immediately, irrespective of the extent of available adverse reaction information. Reporting will be collected on the adverse reaction CRFs, which are to be submitted to Imperial College, Pfizer, MHRA and REC. Adverse reactions should be reported using concise medical terminology on the CRFs as well as on the form for collection of serious adverse reaction information.

## 9. Statistical Analysis

### 9.1 Size of treatment effect

This novel project is a Pilot Phase II double-blinded, placebo controlled randomised (2:1 Axitinib : Placebo) for 50 patients. This sample size would not normally allow for conventional or adequate powering of a study based on OS, PFS or RR. This is a pilot study of assessing efficacy of axitinib monotherapy in colorectal cancer. The primary end-point is PFS by conventional RECIST. If a difference of more than 6 weeks improvement in PFS is observed, then a funding application to Pfizer and UK NCRN will be made for an adequately powered phase III study.

As a secondary and exploratory analysis, the major interest is whether we can better select (or predict) the population that benefits from Axitinib within the next generation of study design. If our secondary hypothesis is correct, then in those patients who receive Axitinib, a significant proportion will have ultrasound detectable changes in reduction in blood flow. i.e. a significant pharmacodynamic effect on the tumour vasculature measured via the US biomarker index (CEPHI). In our preliminary work (Gauthier et al, 2011), a 20% change in CEPHI was significant and also allowed for measurement error. Thus, this study will therefore examine the survival difference between CEPHI responders (those whose CEPHI falls by  $\geq 20\%$ ) versus non-responders. A clinically meaningful difference in survival in these groups would be a difference of at least 6 weeks. If this end-point is achieved, it would be a positive signal to design an adequately powered phase III powered for OS. This would allow enrichment for patients who potentially benefit, but also allow discontinuation in patients at 2 weeks who will not benefit, saving unnecessary treatment and toxicities. This approach of personalised medicine using biomarkers (in this case CEPHI) is the direction of almost all cancer studies.

The conventional PFS and OS for this cohort of chemo-refractory patients is 6-8 weeks and 4-6 months respectively. This is the first study with Axitinib in this setting. Our aim with 50 patients is to generate data for a sample size calculation for a randomised phase III. In the only comparative Phase 2 study (A6181003) with a similar compound, is of Sunitinib in chemorefractory metastatic colorectal cancer, 84 patients were enrolled and 82 were actually treated with Sunitinib. 10% discontinued due to adverse events. The ITT analyses for PFS was less than 2 months but OS still showed an encouraging overall survival of 10.2 months. Of greater interest, 1 patient with prior Bevacizumab therapy had a partial response; 24 patients (29%) had a best response of stable disease, 13 patients had SD  $\geq 22$  weeks. (This demonstrates the reason for doing our analysis as a sub-population has benefited significantly from Axitinib's parent compound and with CEPHI – we hope to predict this group). In our study, we would thus expect around 15-18 of the treated patients to have prolonged progression-free survival of this order of magnitude, and the placebo treated patients will act as a contemporaneous control. If the 2 week CEPHI index is highly predictive of survival in this group, then selection on this basis for a phase III trial will enrich the potentially benefitting population even further.

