## Study Design

A Phase II, double-blind, 2 arm pilot randomised placebo controlled trial. 50 patients will be randomised 2:1 to Axitinib or placebo.

Main Inclusion criteria: Chemo-refractory third-line metastatic CRC with US-assessable liver or other abdominal metastases that can have a baseline DCEUS baseline measurement.

Arm A: Axitinib monotherapy started in all patients at 5mg bd, and increased fortnightly by a dose level (See Table 4) as tolerated to a maximum dose of 10mg bd.

Arm B: Placebo at 2:1 ratio to treatment

Follow up: *Optional* visit at 48-72 hours post first dose for measurement of temperature, oxygen saturations, blood pressure and CEHPI. Outpatient monitoring at 2 weeks and 4 weeks post first dose and at 4 week intervals thereafter which will include medical history and examination, measurement of temperature, oxygen saturations and blood pressure, urinalysis and blood tests including GI profile and VEGF-PK samples. RECIST restaging at 8 weeks and at 8 weekly intervals thereafter. CEHPI will be performed at baseline, optionally at 48-72 hours, 2 weeks and 8 weeks for assessment of differential blood supply. At 8 weeks, after tumour CT RECIST assessments, conventional responders (CR/PR/SD) continue monotherapy. In non-responders (PD), monotherapy can be continued if patient chooses to continue and if tolerated.

[figure not shown]

Figure 1: Protocol for responders and non-responders to Axitinib at 8 week RECIST evaluation.

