### Secondary Endpoints

- To compare overall survival between the treatment and placebo arms
- To compare duration on study treatment between the treatment and placebo arms
- To compare the best overall RECIST response rate between the treatment and placebo arms
- To compare and correlate the 2-week CEHPI perfusion index and 8 week RECIST response rates in the ITT population
- To compare the median overall survival of patients receiving Axitinib who develop new diastolic hypertension ( $>90\text{mmHg}$ ) with those that do not (in either/or the blinded placebo group or treatment group combined)
- To identify if CEHPI will function as a correlative biomarker of Axitinib pharmacokinetics (PK) and help minimise toxicity and identify responders
- To compare toxicity (CTC) information for the treatment and placebo arms.
  - Type, incidence, severity, timing, seriousness of adverse events by Chemotherapy toxicity criteria (CTC) v4.03 grading.
- Axitinib PK analysis correlation with patients developing or not developing diastolic hypertension

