### **5.3 Blinding**

Patients, sonographers and clinicians will be blinded to therapy. Pharmacy will have an anonymised coding ticket system for dispensing drug/ placebo once randomisation is complete. Unblinding will only occur at the discretion of the data monitoring committee or the investigators in an emergency situation (including out-of-hours), primarily for safety reasons throughout the duration of the trial.

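### Section 9.1 reads a drug effect on blood flow from CEHPI falls in the Axitinib arm alone; no planned analysis compares CEHPI change with placebo

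*Combined protocol and SAP*

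**What the plan says.** Section 9.1 (Size of treatment effect) gives the secondary hypothesis as a statement about treated patients: "in those patients who receive Axitinib, a significant proportion will have ultrasound detectable changes in reduction in blood flow". It then glosses this as "a significant pharmacodynamic effect on the tumour vasculature measured via the US biomarker index (CEPHI"). No target proportion and no placebo reference is attached. On the threshold, the same section says that in preliminary work "a 20% change in CEPHI was significant and also allowed for measurement error", without giving an SD, CV or repeatability coefficient. (The documents spell the index both CEHPI and CEPHI; CEHPI is used here.)

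The design would support a comparison of arms. The Trial Summary states that "50 patients will be randomised 2:1 to Axitinib or placebo", and that "CEHPI will be performed at baseline, optionally at 48-72 hours, 2 weeks and 8 weeks", with no restriction by arm; section 7.8 repeats the baseline, 2-week and 8-week scans. Section 5.3 adds: "Patients, sonographers and clinicians will be blinded to therapy".

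The CEHPI endpoints in section 2.2 do not use that comparison. One co-primary endpoint compares PFS by whether CEHPI fell by more than 20%. A secondary endpoint reads "To compare and correlate the 2-week CEHPI perfusion index and 8 week RECIST response rates in the ITT population", and another relates CEHPI to Axitinib pharmacokinetics. Section 9.2 plans log-rank tests of PFS and OS by CEHPI responder status and an ROC analysis against RECIST. Section 9.3 plans a correlation with pharmacokinetics.

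**The concern.** A fall in CEHPI among treated patients is a before-and-after observation. It contains whatever the drug did plus whatever would have happened to anyone scanned twice, two weeks apart, in this disease. A concurrent placebo group separates the two. Here that group is randomised, blinded and due to be scanned, but nothing in the plan sets its CEHPI change beside that of the Axitinib arm.

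What is at stake is the interpretation of the marker. Section 2.2 calls a fall above 20% vascular shutdown. Section 9.1 looks ahead to enriching a phase III trial on the index and to using it for 2-week decisions. Those uses are easier to defend if Axitinib has been shown to cause the fall. They also need the rate at which untreated patients cross 20%, and the planned analyses do not report it.

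**Working it through.** **1. Inputs.** 50 patients at 2:1 gives 50 × 2/3 = 33.3 and 50/3 = 16.7, so about 33 Axitinib and 17 placebo. The threshold is a 20% fall, ln 0.8 = −0.223. The documents give no within-patient CV, no placebo change and no target responder rate; all three are assumptions below. There is no plan figure to reproduce: section 9.1 says of the 50 patients that "This sample size would not normally allow for conventional or adequate powering".

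**2. Where CEHPI change is analysed.**

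| Place | Comparison | Between arms? |
|---|---|---|
| 2.1 and 2.2 | CEHPI against RECIST, placebo patients included | No |
| 2.2 co-primary | PFS by fall above 20% or not | No |
| 2.2 and 9.3 | CEHPI against Axitinib pharmacokinetics | No |
| 9.2 | PFS and OS by CEHPI responder status; ROC cut-point | No |

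**3. What each contrast estimates.** Write ln(CEHPI at 2 weeks / baseline) = s + d × (1 if Axitinib, 0 if placebo) + error, where s is any change common to both arms and d is the drug effect. The Axitinib-arm mean estimates s + d. The placebo mean estimates s. Only the difference between arms estimates d.

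**4. A CV that fits the threshold claim.** If 20% is read as the 95% limit of measurement error, the SD of the log ratio is 0.223/1.96 = 0.114, and the within-patient CV is about 0.114/√2 = 0.08, or 8%.

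**5. Share crossing 20% with no drug effect.** P = Φ[(ln 0.8 − ln(1 + drift)) / SD], with SD = √(2 ln(1 + CV²)). At CV 8%, SD = 0.113.
- No drift: Φ(−0.223/0.113) = 2.4%, and 33 × 0.024 = 0.8 patients.
- Shared 10% fall: Φ((−0.223 + 0.105)/0.113) = 14.9%, and 33 × 0.149 = 4.9 patients.

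Over a range of assumed CVs, expected crossings among 33 Axitinib patients with no drug effect are:

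| CV | No drift | Shared 10% fall |
|---|---|---|
| 5% | 0.1% (0.0) | 4.8% (1.6) |
| 8% | 2.4% (0.8) | 14.9% (4.9) |
| 10% | 5.7% (1.9) | 20.2% (6.7) |
| 15% | 14.5% (4.8) | 28.8% (9.5) |
| 20% | 21.3% (7.0) | 33.7% (11.1) |

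The rows above 8% apply only if the threshold does not in fact cover measurement error in the sense of step 4.

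**6. The other direction.** Section 1.2 says that tumour growth in the liver draws on arterial flow, so CEHPI might rise in untreated patients. If the drug multiplied CEHPI by 0.80 and the shared change multiplied it by 1.10, the observed ratio would be 0.80 × 1.10 = 0.88. That is a 12% fall, which would not reach the threshold although the drug worked.

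**7. What the missing contrast could deliver.** For mean log change, 80% power at two-sided 0.05 needs a difference of (1.960 + 0.842) × √(1/17 + 1/33) = 0.84 SD. For responder proportions, assuming 50% on Axitinib:
- against 5% on placebo, power is 0.95 (Fisher's exact 0.93);
- against 15%, 0.70 (0.61);
- against 30%, 0.26 (0.20).

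**The case against.** The sentence in section 9.1 is conditional rationale within a secondary and exploratory aim. Sections 9.2 and 9.3 contain no one-sample test, no target proportion and no rule for declaring a pharmacodynamic effect. A reader might infer that the plan would declare a drug effect falsely at some calculable rate. The documents do not support that, because no such procedure is written. This stands, and it makes the defect an omission.

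A reader might also infer that regression to the mean will produce falls in CEHPI. No eligibility criterion in section 4 selects on a high baseline value, so no group-level shift from selection is expected. Pure noise matters little if the 20% threshold does what section 9.1 says: step 5 gives under one patient at CV 8%. Fasting, scanner settings and a control-artery reading are standardised (section 7.8, Appendix 5), which limits technical drift. Nothing in the documents shows that a shared fall will occur.

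Placebo patients are not ignored. They enter the CEHPI-against-RECIST analysis, and section 9.1 calls them a contemporaneous control, but in a sentence about prolonged PFS. Neither use is a comparison of CEHPI change by arm. The pharmacokinetic correlation offers some exposure-response evidence, but exposure is not randomised and doses are titrated on tolerance (section 5.8).

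Finally, the signal for phase III in section 9.1 is a survival difference of at least 6 weeks between CEHPI responders and non-responders, not the rate of CEHPI falls. That also stands. It limits the consequence but does not supply the missing evidence that the drug moves the index.

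**Conclusion.** The point holds as an omitted comparison. Section 9.1 equates a CEHPI fall in treated patients with a drug effect, and no endpoint or analysis tests CEHPI change against placebo, although the data should exist in both arms under blinded assessment. As worded, the inference cannot separate drug effect from shared change, which could exaggerate or mask it. The 20% threshold addresses error in a single patient's reading, with no supporting figure, and does not address shared drift.

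The size cannot be taken from the documents. Under an assumed CV of 8% and no drug effect, about 1 of 33 Axitinib patients would cross 20% without drift and about 5 of 33 with an assumed shared 10% fall. These are illustrations, not predictions.

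A reader might infer that adding the contrast would validate CEHPI for selecting patients. It would not. It shows whether Axitinib changes the index; whether CEHPI responders benefit from the drug is a separate, treatment-by-biomarker question.

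**What to change.** Restate the pharmacodynamic hypothesis in section 9.1 as a difference between Axitinib and placebo. Add to sections 2.2 and 9.2, as a secondary analysis:
- 2-week log(CEHPI) compared between arms as randomised, by ANCOVA with baseline log(CEHPI) as covariate, reported as a ratio with 95% CI;
- the proportion with a fall above 20% in each arm, and the difference between arms with 95% CI.

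State that any claim of a pharmacodynamic effect rests on this contrast, and that the contrast alone does not show benefit in CEHPI responders.

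The cost is a change of wording and one extra analysis of data already scheduled. The drawback is precision: with about 17 placebo patients, the comparison of proportions is informative if few placebo patients cross 20% and weak if about 30% do (step 7). The intervals should therefore carry the interpretation, and a non-significant result should not be read as no effect.

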**Early Biomarkers of response are needed to rapidly select responders and help design new paradigms of clinical benefit.**

The lack of validated and reproducible VEGF response biomarkers makes study of the optimal use of VEGF inhibitors time consuming for conventional RECIST end-points. We have developed a simple technique using differential liver blood flow assessments using microbubble (dynamic contrast-enhanced ultrasound) for liver tumours (primary and secondary) which appears promising. This imparts information akin to dynamic contrast-enhanced MRI, but is cheaper, portable and much easier to perform serially. Measuring perfusion characteristics across individual liver lesions has problems with reproducibility and a bias towards larger, more visible lesions. This is the result of liver including metastases having a dual blood supply with dynamic shifts in differential distribution between the metastases. To overcome this we have developed summation technology across the whole liver, measuring the ratios of arterial to portal venous flow [ENREF 9](#). This is termed the Contrast Enhanced Hepatic Perfusion Index (CEHPI). This is able to analyse differential blood flow in liver metastases that are responding and also detect differences in the distributable flow from the portal vein and hepatic artery. It is known that the neo-angiogenesis that supports the growth of malignant tumours in the liver, preferentially sources this from the hepatic artery (as opposed to the portal vein, which is the dominant source of blood to normal liver parenchyma). We have preliminary data that suggests that this trend is reversed towards normal liver portal venous flow in responding tumours with both cytotoxic chemotherapy and VEGF inhibitors including Bevacizumab.

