## 9.2 Statistical analysis plan

The primary analysis will be on PFS by Kaplan-Meier of patients who manage to complete at least 2 weeks of Axitinib therapy (versus Placebo).

For the secondary analyses:-

A stratified log-rank test (1-sided,  $p=0.025$ ) will be used to compare PFS between CEHPI responders and non-responders. The median event time and 2-sided 95% CI for the median will be provided. The hazard ratio and its 95% CI will be also estimated.

The optimum CEHPI cut-point for determining response will be confirmed using the percentage change in CEHPI against RECIST response using a receiver operator characteristic curve. Test statistics including sensitivity, specificity, positive predictive value, negative predictive value, odds of disease progression and area under the curve will be calculated for 2 week CEHPI reduction in predicting disease progression.

A similar analysis will be performed with diastolic blood pressure.

Overall survival is defined as the time from date of randomisation to date of death due to any cause. For patients not expiring, their survival times will be censored at the last date they are known to be alive. Patients lacking data beyond the day of randomisation will have their survival times censored at the date of randomisation with duration of 1 day. Overall survival will be summarised using Kaplan-Meier methods and displayed graphically where appropriate. A stratified log-rank test (1-sided,  $p=0.025$ ) will be used to compare OS between CEHPI responders and non-responders. The median event time and 2-sided 95% CI for the median will be provided. The hazard ratio and its 95% CI will be also estimated.

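### The 6-week CEHPI responder gap in section 9.1 has no Axitinib-versus-placebo contrast, so it can show a prognostic association but cannot identify who does or does not benefit from Axitinib

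*Combined protocol and SAP*

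**What the plan says.** Section 9.1 asks whether the population that gains from Axitinib can be selected, and labels this work secondary and exploratory. The comparison is between marker groups, defined by a 20% fall in CEHPI at 2 weeks: "this study will therefore examine the survival difference between CEPHI responders" and non-responders. The threshold is "A clinically meaningful difference in survival in these groups would be a difference of at least 6 weeks". The consequence is "If this end-point is achieved, it would be a positive signal to design an adequately powered phase III powered for OS", followed by the statement on enrichment and discontinuation: "This would allow enrichment for patients who potentially benefit, but also allow discontinuation in patients at 2 weeks who will not benefit". Later, section 9.1 adds "If the 2 week CEPHI index is highly predictive of survival in this group, then selection on this basis for a phase III trial" as a way to enrich further.

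Section 9.2 supplies the tests. A one-sided 0.025 log-rank test, called stratified although no strata are named, "will be used to compare PFS between CEHPI responders and non-responders". A second such test "will be used to compare OS between CEHPI responders and non-responders". Medians, hazard ratios and 95% CIs accompany both. Section 2.2 lists the PFS version as a co-primary endpoint, which sits awkwardly with the exploratory label.

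Three other statements involve placebo:
- Section 9.1 has a separate Axitinib-versus-placebo PFS rule (an improvement of more than 6 weeks) and calls the placebo patients a contemporaneous control.
- The secondary objectives include placebo patients in the CEHPI–RECIST analysis.
- The trial summary in the GP letter (Appendix 4) compares survival of Axitinib responders with Axitinib non-responders and with placebo.

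**The concern.** Benefit means doing better on the drug than without it. A comparison of marker groups that ignores arm does not address that. It cannot show that responders outlive similar patients on placebo, or that non-responders do no better than placebo.

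The protocol's rationale leaves room for a marker that is only prognostic. Section 1.2 links arterial supply to tumour growth and reports the shift back to portal flow "in responding tumours with both cytotoxic chemotherapy and VEGF inhibitors including Bevacizumab", so the change is not specific to VEGF inhibition. A patient with slower disease might show a CEHPI fall on either arm and live longer on either arm.

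What is at stake is the population of the next trial. If Axitinib helps nobody, the gap could still prompt an enriched phase III. If it helps both CEHPI groups equally, the gap could lead to the exclusion of patients who would gain.

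**Working it through.** **Inputs from the documents.** 50 patients at 2:1, about 33 and 17; background PFS 6–8 weeks and OS 4–6 months (17.4–26.1 weeks); gap threshold 6 weeks. The plan gives no power for the CEHPI rule, so there is no figure of its own to reproduce. Section 9.1 says only survival, so both OS and PFS are checked.

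**How strong must a prognostic marker be?** Under exponential survival with non-responder median m, a true 6-week gap in medians needs a hazard ratio (HR) of m/(m+6):
- OS 4 months: 17.39/23.39 = 0.74. OS 6 months: 26.09/32.09 = 0.81.
- PFS 6 weeks: 6/12 = 0.50. PFS 8 weeks: 8/14 = 0.57.

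A modest association is enough on OS; a strong one is needed on PFS.

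**How often does a null drug meet the threshold?** Assumptions: drug effect exactly zero, CEHPI response independent of arm, 40% responders, the same prognostic HR in both arms, exponential times, no censoring, and non-responder medians at the plan's background figures; 6,000 trials per scenario. Percentage of trials with an observed median gap of at least 6 weeks:

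| Prognostic HR | OS, all 50 | OS, Axitinib only | PFS, all 50 | PFS, Axitinib only |
|---|---|---|---|---|
| 1.0 | 20.6–28.8 | 24.5–32.2 | 1.5–4.7 | 3.2–7.7 |
| 0.74 | 51.0–59.2 | 49.2–58.5 | 10.9–21.2 | 16.0–27.1 |
| 0.6 | 71.2–78.4 | 67.2–73.6 | 29.4–44.7 | 32.1–45.2 |
| 0.5 | 84.6–88.7 | 79.8–84.1 | 48.8–64.1 | 48.8–63.0 |

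**Sensitivity.**
- OS with 50% responders, the whole cohort's median set to 17.3–26 weeks, and censoring between 52 and 130 weeks: at HR 0.6, 61–70% (Axitinib only) and 65–75% (pooled); at HR 1.0, 24–33% (Axitinib only).
- PFS with the whole cohort's median set to 6–8 weeks: at HR 0.6, about 19–37%.
- OS at 4 months, all 50, with 30% or 50% responders: 82.2% or 85.9% at HR 0.5, and 22.7% or 19.4% at HR 1.0.
- The PFS runs use continuous event times. Progression will be read at 8-weekly scans, so these figures are approximate.

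**Does the log-rank test repair it?** No. At HR 0.5, all 50 patients, requiring both the gap and one-sided p<0.025 still passes 60–61% on OS and 43–53% on PFS. If arm were one of the unnamed strata, the test would still compare responders with non-responders within arm; on OS with 50% responders it rejects in about 37% at HR 0.6.

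**Does the GP-letter comparison repair it?** No. At a 4-month non-responder OS median and HR 0.5, with a null drug, responders have median 17.39/0.5 = 34.8 weeks. All placebo patients, 40% of them responders, have median t solving 0.6·2^(−t/17.39) + 0.4·2^(−t/34.78) = 0.5, so t = 22.5. The gap is about 12 weeks without any drug effect.

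**What does an arm contrast do?** In these null-drug scenarios a one-sided 2.5% arm-by-CEHPI interaction test passes in about 3–4%, whatever the prognostic strength. Its power is low. With 40% responders in both arms and all 50 events, SE(log HR ratio) = √(1/13.2 + 1/19.8 + 1/6.8 + 1/10.2) = 0.61, and power for an HR ratio of 0.5 is Φ(0.693/0.61 − 1.96) ≈ 21%. With 50% responders and CEHPI acting only on Axitinib, simulated power is 14%, 19% and 31% for HR 0.6, 0.5 and 0.4. If only 10% of placebo patients respond, the SE is √(1/13.2 + 1/19.8 + 1/1.7 + 1/15.3) = 0.88 and power falls to about 12%.

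**The case against.** **Status of the claim.** A reader might infer that the plan declares Axitinib effective in CEHPI responders. It does not. The analysis is labelled exploratory, the study is acknowledged to be unpowered, and the benefit in responders is hedged as potential. Nor is treatment in this trial stopped on CEHPI: the design continues responders after the 8-week RECIST assessment, and even patients with progression may continue. This lowers the stakes, but the wording about patients who will not benefit is unhedged, and section 2.2 makes the PFS version co-primary.

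**The arm-level rule.** The Axitinib-versus-placebo PFS result would be reported alongside, so the drug would not be judged on CEHPI alone. That stands. However, the CEHPI rule does not depend on that result, and section 9.2 contains no CEHPI analysis that uses placebo as a contrast.

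**Certainty of a false signal.** A reader might infer that any prognostic marker passes. It is a probability: high on OS, but at HR 0.6 the PFS rule usually fails. Part of the OS rate is noise in a median gap judged without a CI, as the HR 1.0 row shows. The simulations also assume that placebo patients become CEHPI responders as often as Axitinib patients. Section 1.2 reports the shift only in tumours responding to active treatment, so that share is uncertain.

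**An interaction test as the new rule.** It is tempting to say that CEHPI marks benefit if its association is stronger on Axitinib. That is not sound either. CEHPI is measured after randomisation. If Axitinib lowers CEHPI mainly in good-prognosis patients without changing survival, while placebo changes are noise, a real interaction appears with zero benefit. The dichotomised contrast may also be inestimable: with 17 placebo patients, the chance of at most one responder is 0.9^17 + 17·0.1·0.9^16 ≈ 48% at a 10% rate, and 79% at 5%.

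**Conclusion.** The point holds as a mismatch between question and comparison, and that part needs no assumed numbers: section 9.1 asks who benefits from Axitinib and answers with a contrast that omits treatment arm. A 6-week gap shows at most a prognostic association.

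With a null drug and an assumed prognostic HR of 0.6, the gap appears in roughly 60–78% of trials on OS and 19–45% on PFS; with no association, in about 19–33% and 1–8%. These sizes rest on assumed hazard ratios, responder shares and exponential survival. The documents do not support the stronger readings that the plan declares benefit, that the rule always passes, or that patients in this trial lose treatment because of it. It should be corrected because it shapes what the trial can claim and whom phase III would enrol.

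**What to change.** **Section 9.2.** Add one Cox model for PFS and one for OS, landmarked at the 2-week scan, with arm, 2-week percentage change in CEHPI and their interaction. Keep CEHPI change continuous, with the 20% cut as a secondary display. Report the CEHPI hazard ratio in each arm and the ratio of the two with its 95% CI, as hypothesis-generating estimates and not as a pass/fail rule.

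**Section 9.1.** Delete the inference that a 6-week gap identifies patients who will not benefit or by itself supports enrichment. State that the gap alone shows a prognostic association, and would support a phase III that randomises both CEHPI groups with CEHPI as a stratum or planned subgroup. This concerns what the comparison can show; it proposes no treatment rule.

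**Cost.** Wording plus two models on data already scheduled in both arms; no new patients or procedures. Interaction power is about 14–31% even with half of placebo patients responding, and lower if few do, so the usual result will be a wide interval. Because the marker is post-randomisation, even a clear interaction is only supportive.
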